### **11.7 Handling of Biological Specimens**

Not applicable.

### **11.8 Publications**

Authorship and manuscript composition will reflect cooperation among all parties involved in the trial. Authorship will be established before writing the manuscript. The trial sponsor will have the final decision regarding authorship, manuscript and publication.

### 13 APPENDICES

#### Appendix 1 Schedule of Assessments (in recommended order)

Procedure	Visit 1  (Day1)	Visit 2 (week 4 ± 2 days)	TC 1 (week 8 ± 2 days)	Visit 3 (week 12 ± 7 days)	TC 2 (week 16 ± 7 days)	TC 3 (week 22 ± 7 days)	Visit 4 (week 26 ± 7 days)	TC4 (week 30 ± 7 days)	TC5 (week 36 ± 7 days)	Visit 5 (week 40 ± 7 days)	TC 6 (week 44 ± 7 days)	TC 7 (week 48 ± 7 days)	Visit 6/ET (week 52 ± 7 days)
Informed Consent / HIPAA	X 												
Medical/ Surgical History and Demographics	X 												
Concomitant Medication	X 	X	X	X	X	X	X	X	X	X	X	X	X
Inclusion/Exclusion Criteria	X 												
Urine Pregnancy Test (as needed) 	X 	X		X			X			X			X
Dryness Score (VAS severity of dryness)	X 	X		X			X			X			X
VAS	X 	X		X			X			X			X
OSDI	X 	X		X			X			X			X
Eyedrop Comfort and Acceptability Questionnaire													X
Visual Acuity (ETDRS)	X 	X		X			X			X			X
Slit-Lamp Biomicroscopy	X 	X		X			X			X			X
TFBUT	X 	X		X			X			X			X
Corneal Fluorescein Staining (NEI scale)	X 	X		X			X			X			X
Meibomian Gland Assessment (MGD score)	X 	X		X			X			X			X
Schirmer's Test I (without anesthesia)	X 						X						X
Intraocular Pressure	X 	X		X			X			X			X
Dilated Fundoscopy	X 			X			X			X			X
Adverse Event Query	X 	X	X	X	X	X	X	X	X	X	X	X	X
In-office instillation trial medication	X 												
Dosing Diary Dispensation/Review/Collection	X 	X		X			X			X			X
Dispensation of trial medication	X 			X			X			X			
Collection of trial medication				X			X			X			X
Trial Exit													X

 For women of childbearing potential

 For subjects continuing from NVU-003 to NVU-004, V1 of NVU-004 will be performed at V4 (Day 57) of NVU-003.

 Assessment Results being transferred from NVU-003 V4 (Day 57) to NVU-004 V1 (Day 1)

 Assessments to be performed for NVU-004

[figure not shown]
ETDRS = Early Treatment of Diabetic Retinopathy Study; HIPAA = Health Information Portability and Accountability Act; NEI = National Eye Institute; OSDI = Ocular Surface Disease Index; TFBUT = Tear Film Break Up Time; ET= Early Termination; VAS: burning/stinging, sticky feeling, foreign body sensation, itching, blurred vision, sensitivity to light, pain, frequency of dryness, and awareness of dry eye symptoms

## Appendix 2 Instructions for Administration of Eye Drops

### Instructions for Use

Subjects will be instructed to instill one drop in each eye four times daily and as illustrated below. Subjects will be instructed to use a second drop only if the first drop misses the eye. Subjects will be given detailed instructions on study drug administration (see below), accountability, and storage.

### Proper Handling of Eye drop Container

#### Figure A. Opening the bottle

1. Unscrew the cap of the bottle.
2. Prior to the first administration of the study drug you must separate the cap from the safety seal ring below the cap and remove the safety seal ring.
3. Do not touch the dropper after removing the cap.
4. To avoid loss of solution **please read steps 5 to 7** carefully before applying the eye drops.
5. Hold the opened bottle with the dropper pointing upwards and gently press the bottle between thumb and index finger.
6. Keep the bottle under slight pressure and turn the bottle until the dropper points downwards.
7. With the dropper pointing downwards reduce the pressure on the bottle to allow some air to flow into the bottle.

#### Figure B. Instilling the drop

1. Lean your head back slightly and carefully pull down your lower eyelid. Look upwards.
2. Hold the opened bottle with the dropper pointing downwards above your eye. Apply gentle pressure on the bottle and administer 1 drop per eye. Note: Due to the special properties of the study drug you may not feel the drop falling into your eye. In this case we recommend application in front of a mirror.
3. Do not touch the dropper with your eye or lashes.
4. For an even distribution, close your eyes after applying the study drug.
5. Put the screw cap back on after administration.

If a subject has difficulties with step 4 to 7 of Figure A, advise to refer to step 2 of Figure B: subject to squeeze bottle very gently or to wait until drop drips from the bottle without squeezing.

### Appendix 3 Examination Procedures, Tests, Equipment, and Techniques

[figure not shown]
The following examination procedures, tests, equipment and techniques are listed in this Appendix:

- Dryness Score (VAS Severity of Dryness)
- Visual Analog Scale (VAS)
- Ocular Surface and Disease Index (ODSI®) questionnaire
- Visual Acuity
- Slit-Lamp Biomicroscopy
- Tear Film Break-up Time (TFBUT)
- Fluorescein Staining (NEI/Industry workshop Scale)
- Meibomian Gland Assessment (MGD score)
- Schirmer's Test I (without anesthesia)
- Procedure for Evaluating Intraocular Pressure
- Procedure for Conducting Dilated Fundoscopy
- Eyedrop Comfort and Acceptability Questionnaire
- Dosing Diary

#### Dryness Score

Study staff will ask subjects to rate their severity of ocular dryness (both eyes simultaneously) by placing a vertical mark on the horizontal line to indicate the level of discomfort (0 corresponds to “no dryness” and 100% corresponds to “maximal dryness”). The assessment line length of the scale will be 100 mm (10 cm) and will be according to the following depiction:

Please rate this symptom by placing a vertical mark on the horizontal line to indicate the level of discomfort associated with dryness. 0% corresponds to “no discomfort” and 100% corresponds to “maximal discomfort”.

## Ocular Surface and Disease Index (OSDI)® questionnaire

### Ocular Surface Disease Index® (OSDI)®

Ask your patients the following 12 questions, and circle the number in the box that best represents each answer. Then, fill in boxes A, B, C, D, and E according to the instructions beside each.

Have you experienced any of the following during the last week ?	All of the time	Most of the time	Half of the time	Some of the time	None of the time
1. Eyes that are sensitive to light? . . .	4	3	2	1	0
2. Eyes that feel gritty? . . . . .	4	3	2	1	0
3. Painful or sore eyes? . . . . .	4	3	2	1	0
4. Blurred vision? . . . . .	4	3	2	1	0
5. Poor vision? . . . . .	4	3	2	1	0

Subtotal score for answers 1 to 5

Have problems with your eyes limited you in performing any of the following during the last week ?	All of the time	Most of the time	Half of the time	Some of the time	None of the time	N/A
6. Reading? . . . . .	4	3	2	1	0	N/A
7. Driving at night? . . . . .	4	3	2	1	0	N/A
8. Working with a computer or bank machine (ATM)? . . . . .	4	3	2	1	0	N/A
9. Watching TV? . . . . .	4	3	2	1	0	N/A

Subtotal score for answers 6 to 9

Have your eyes felt uncomfortable in any of the following situations during the last week ?	All of the time	Most of the time	Half of the time	Some of the time	None of the time	N/A
10. Windy conditions? . . . . .	4	3	2	1	0	N/A
11. Places or areas with low humidity (very dry)? . . . . .	4	3	2	1	0	N/A
12. Areas that are air conditioned? . . .	4	3	2	1	0	N/A

Subtotal score for answers 10 to 12

Add subtotals A, B, and C to obtain D  
 (D = sum of scores for all questions answered)

Total number of questions answered  
 (do not include questions answered N/A)

[figure not shown]
Please turn over the questionnaire to calculate the patient's final OSDI® score.

## Evaluating the OSDI® Score

The OSDI® is assessed on a scale of 0 to 100, with higher scores representing greater disability. The index demonstrates sensitivity and specificity in distinguishing between normal subjects and patients with dry eye disease. The OSDI® is a valid and reliable instrument for measuring dry eye disease (normal, mild to moderate, and severe) and effect on vision-related function.

## Assessing Your Patient’s Dry Eye Disease

Use your answers D and E from side 1 to compare the sum of scores for all questions answered (D) and the number of questions answered (E) with the chart below.\* Find where your patient’s score would fall. Match the corresponding shade of red to the key below to determine whether your patient’s score indicates normal, mild, moderate, or severe dry eye disease.

1. Data on file, Allergan, Inc.  

## Visual Acuity Procedures

LogMAR Visual Acuity (VA) must be assessed using an ETDRS-like chart. The procedure used will be consistent with the recommendations provided for using the ETDRS eye charts. Visual Acuity should be evaluated at the beginning of each visit in the study (i.e. prior to slit-lamp examination). Subjects should use the most recent correction to attain their best-corrected visual acuity (BCVA) during all VA assessments. Pinhole testing is not permitted.

## Equipment

The visual acuity chart to be used is the ETDRS chart. In ALL cases, for purposes of standardizing the testing conditions during the study, all sites must use only ETDRS Series 2000 Chart 1 & 2, and the right eye (OD) should be tested first. For reflectance (wall) charts,

the chart should be placed frontally and well illuminated. The subject viewing distance should be exactly 4 meters (13 feet).

### Measurement Technique

The chart should be at a comfortable viewing angle. The right eye should be tested first. The subject should attempt to read each letter, line-by-line, left to right, beginning with line 1 at the top of the chart. The subject should be told that the chart has letters only, no numbers. If the subject reads a number, he/she should be reminded that the chart contains no numbers, and the examiner should then request a letter in lieu of the number. The subject should be asked to read slowly, so as to achieve the best identification of each letter. He/she is not to proceed to the next letter until he/she has given a definite response.

If the subject changes a response (e.g. 'that was a "C" not an "O"') before he/she has read aloud the next letter, then the change must be accepted. If the subject changes a response having read the next letter, then the change is not accepted. The examiner should never point to the chart or to specific letters on the chart during the test.

A maximum effort should be made to identify each letter on the chart. When the subject says he/she cannot read a letter, he/she should be encouraged to guess. If the subject identifies a letter as one of two letters, he/she should be asked to choose one letter and, if necessary, to guess. When it becomes evident that no further meaningful readings can be made, despite encouragement to read or guess, the examiner should stop the test for that eye. However, all letters on the last line should be attempted as letter difficulties vary and the last may be the only one read correctly. The number of letters missed or read incorrectly should be noted.

### LogMAR Visual Acuity Calculations

The last line in which a letter is read correctly will be taken as the base logMAR reading. To this value will be added the number "N x 0.02" where 'N' represents the total number of letters missed up to and including in the last line read. This total sum represents the logMAR visual acuity for that eye.

For Example: Subject correctly reads 4 of 5 letters on the 0.2 line, and 2 of 5 letters on the 0.1 line.

Base logMAR	= 0.1
N (total number of letters incorrect on line 0.2 and on line 0.1)	= 4
N x T (T=0.02)	= 0.08
Base logMAR + (N x T)	= 0.1 + 0.08
logMAR VA	= 0.18

Repeat the procedure for the left eye (OS).

In order to provide standardized and well-controlled assessments of visual acuity during the study, all visual acuity assessments at a single site must be consistently done using the same lighting conditions and same correction if possible during the entire study. If the same correction cannot be used (i.e. a subject forgets his/her glasses), the reason for the change in correction should be documented.

Note: A clinically significant visual acuity decrease (defined as an increase of 0.22 or greater in logMAR score) from Visit 0 (NVU-003) will be considered an Adverse Event.

### **Slit-Lamp Biomicroscopy**

Slit-lamp biomicroscopy will be performed during the study. Observations will be graded as *Normal* or *Abnormal*. Abnormal findings, which are clinically significant, will be described. The following will be examined at each visit:

- Lids
- Cornea
- Conjunctiva
- Anterior Chamber
- Iris
- Lens

External magnification and biomicroscopy will be performed using a slit-lamp.

Magnification will be consistent with standard clinical practice. The subject will be seated for the assessment.

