#### Secondary Safety Analyses

Other safety endpoints including visual acuity, slit-lamp biomicroscopy, dilated funduscopy, and intraocular pressure will be summarized by visit using descriptive statistics by treatment group as assigned in NVU-003 and overall. For assessments performed by eye, study eye and fellow eye will be summarized separately. Changes or shifts from baseline (baseline as defined in NVU-003) will be summarized where appropriate.

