**Subjects must not:**

1. Have permanently discontinued investigational medicinal product during NVU- 003 for any reason.

2. Have any clinically significant slit-lamp findings or ocular condition at Visit 1 and/or in the opinion of the investigator have any findings that may interfere with trial parameters.
3. Have an ocular or periocular malignancy.
4. Have a history of herpetic keratitis.
5. Have any planned ocular and/or lid surgeries over the trial period.
6. Be a woman who is pregnant or planning a pregnancy.
7. Be unwilling to submit to a urine pregnancy test at Visit 2, 3, 4, 5 and Visit 6 (or early termination visit) if of childbearing potential. Non-childbearing potential is defined as a woman who is permanently sterilized (e.g. has had a hysterectomy or bilateral tubal ligation or bilateral oophorectomy) or is post-menopausal (without menses for 12 consecutive months).
8. Be a woman of childbearing potential who is not using an acceptable means of birth control; acceptable methods of contraception include: hormonal – oral, implantable, injectable, or transdermal contraceptives; mechanical – spermicide in conjunction with a barrier such as a diaphragm or condom; intrauterine device (IUD); or surgical sterilization of partner. For non-sexually active females, abstinence may be regarded as an adequate method of birth control; however, if the subject becomes sexually active during the trial, she must agree to use adequate birth control as defined above for the remainder of the trial.
9. Have a known allergy and/or sensitivity to the investigational medicinal product (IMP).
10. Be currently enrolled in an investigational drug or device trial other than NVU-003 and NVU-004.
11. Have corrected visual acuity worse than or equal to logarithm of the minimum angle of resolution (logMAR), +0.7 as assessed by Early Treatment of Diabetic Retinopathy Study (ETDRS) scale in both eyes at Visit 1.
12. Have a condition or be in a situation which the investigator feels may put the subject at significant risk, may confound the trial results, or may interfere significantly with the subject's participation in the trial.

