### **10.4 Statistical Analysis**

#### **10.4.1 General Considerations**

Quantitative variables will be summarized using number of subjects (n), mean, median, standard deviation, minimum and maximum. Qualitative variables will be summarized using counts and percentages.

Summaries will be provided for demographics, medical history, concurrent therapies, and subject disposition.

For the purpose of summarization, medical history, concurrent therapies, and AEs will be coded to MedDRA and WHO Drug dictionaries, as appropriate.

Presentation will be by treatment group for subjects treated with NOV03 in NVU-003 and subjects treated with the saline comparator in NVU-003 as well as overall.

The results of assessments performed at multiple visits will be presented by visit as appropriate unless otherwise specified.

The results of bilateral ocular assessments will be summarized separately for study and fellow eyes.

Baseline measures are defined as the measure prior to the administration of IMP in the double masked trial NVU-003, e.g. baseline in NVU-003 and NVU-004 are identical. CFB will be calculated as Value at Follow-up Visit – Value at Baseline Visit.

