#### 10.4.6 Secondary Safety Analyses

Other safety endpoints including visual acuity, slit-lamp biomicroscopy, dilated funduscopy, and intraocular pressure will be summarized by visit and by treatment group as received in NVU-003 using descriptive statistics. Changes from baseline (baseline as defined in clinical trial NVU-003) will also be summarized where appropriate. For assessments performed by eye, study eye and fellow eye will be summarized separately.

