### NEI/Industry Workshop Scale

For each eye, score each of the five areas of the cornea.

[figure not shown]

Diagram of the division of the corneal surface for measuring fluorescein uptake. A standardized grading system of 0-3 is used for each of the five areas on each cornea. Grade 0 will be specified when no staining is present. The maximum total score for each eye is 15.

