### Meibomian Gland Assessment (MGD score)

Meibomian gland dysfunction (MGD) is blockage or some other abnormality of the meibomian glands causing an insufficient secretion of lipids into the tear film. This causes the tears to evaporate too quickly, and thus MGD is considered a leading cause of dry eye syndrome.

The Meibomian Gland Evaluator stick (Korb MGE®-Stick) with standardized force application will be used for this assessment. The Meibomian Gland Assessment (MGD Score) will be performed during the trial at Visits 1 (transferred from V4 of NVU-003), 2, 3, 4, 5 and 6 or at an Early Termination Visit.

The secretion of 5 central glands on the lower eyelid will be evaluated for each eye. Each of the 5 glands will be scored from 0-3: **0 = normal, 1 = thick/yellow, whitish, particulate; 2 = paste; 3 = none/occluded.** The total score will thus range from 0-15.

In the NVU-003 study, i.e. as described in the subject's inclusion criteria, Meibomian Gland Dysfunction is defined as MGD score  $\geq 3$ .

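### The two-level slit-lamp grade cannot show a new clinically significant finding in a structure that was already Abnormal at the NVU-003 baseline

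*Combined protocol and SAP*

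**What the plan says.** Appendix 3 (Slit-Lamp Biomicroscopy) lists lids, cornea, conjunctiva, anterior chamber, iris and lens. On the scale it says: "Observations will be graded as *Normal* or *Abnormal". It then adds: "Abnormal findings, which are clinically significant, will be described". It defines no severity level and no coded category for clinical significance.

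The synopsis (Secondary Safety Analyses) plans the summary this way: "Changes or shifts from baseline (baseline as defined in NVU-003) will be summarized where appropriate". Section 10.4.6 is close to this but does not mention shifts: "Changes from baseline (baseline as defined in clinical trial NVU-003) will also be summarized where appropriate". Section 10.4.1 fixes the reference point: "Baseline measures are defined as the measure prior to the administration of IMP in the double masked trial NVU-003". The comparison is therefore with diseased eyes before any trial treatment.

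Two further passages matter. Exclusion 2 in section 5.4 bars subjects who "Have any clinically significant slit-lamp findings or ocular condition at Visit 1", so abnormality below that threshold may enter. Appendix 3 (Meibomian Gland Assessment) says that in NVU-003 "Meibomian Gland Dysfunction is defined as MGD score" of at least 3.

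**The concern.** A two-level scale can register worsening only in a structure that starts Normal. If a lid or cornea is Abnormal at the NVU-003 baseline, a later finding of any seriousness leaves its grade unchanged. The same happens to a structure that was Abnormal at baseline, Normal at NVU-004 Day 1 and Abnormal again later: against the chosen baseline it shows no change.

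Lids, cornea and conjunctiva are the tissues an eye drop reaches first, and the first two are the ones most likely to be abnormal in this population. The slit-lamp summary would then be least informative where a reader looks for local harm. Section 10.4.10 uses the same safety analyses for the 26-week report behind the initial NDA, so the limit applies to that report too.

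**Working it through.** **Step 1: what each combination of grades shows.**

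| NVU-003 baseline | Later visit | Reads as |
|---|---|---|
| Normal | Abnormal | Worsening |
| Abnormal | Abnormal, same finding | No change |
| Abnormal | Abnormal, new clinically significant finding | No change |

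The last two rows cannot be told apart from the grade. Only the written description separates them, and neither the synopsis nor section 10.4.6 plans a summary of that text.

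**Step 2: is Abnormal at baseline plausible?** The MGD score sums five glands, each 0 to 3 with 0 as normal. A total of at least 3 means at least one examined gland was not normal. This makes an Abnormal lid grade plausible but does not establish it, because the score grades expressed secretion and not the lid as seen at the slit lamp. No staining threshold for NVU-003 entry is given. The baseline share is therefore unknown.

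**Step 3: the plan's own figure.** Section 10.3 claims a 95% or greater chance of observing adverse events with a true rate of 3.0% among 100 completers. This reproduces: 1 − 0.97^100 = 0.952.

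**Step 4: illustration for the shift summary.** Let w be the true rate of worsening in a structure and a the share already Abnormal at baseline. If worsening is independent of baseline grade, the visible rate is w(1 − a), and the chance of at least one visible shift among n subjects is 1 − [1 − w(1 − a)]^n. Here w = 3% is borrowed from section 10.3 as a yardstick only, and a is assumed. The two values of n are the 100 completers and about 200 subjects in the Safety Set (sections 10.1 and 10.3).

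| Assumed a | Visible rate | n = 100 | n = 200 |
|---|---|---|---|
| 0% | 3.00% | 95.2% | 99.8% |
| 25% | 2.25% | 89.7% | 98.9% |
| 50% | 1.50% | 77.9% | 95.1% |
| 75% | 0.75% | 52.9% | 77.8% |
| 90% | 0.30% | 26.0% | 45.2% |
| 100% | 0% | 0% | 0% |

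Example: for a = 50% and n = 100, 1 − 0.985^100 = 0.779. Fixing the number at risk gives nearly the same answers. With 50 or 10 at risk out of 100, 1 − 0.97^50 = 78.2% and 1 − 0.97^10 = 26.3%. With 100 or 20 at risk out of 200, the results are 95.2% and 1 − 0.97^20 = 45.6%.

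**Step 5: what else would catch the finding.**

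- *Adverse events.* Section 9.1 covers unfavourable signs observed by the physician. Section 10.4.5 tabulates ocular events by maximal severity, at subject and eye level. However, worsening of dry eye disease counts only if it goes beyond the subject's previous experience. Visual acuity has a numerical trigger for an adverse event, and slit-lamp findings have none.
- *Corneal staining.* "A standardized grading system of 0-3 is used for each of the five areas on each cornea" The score covers fluorescein uptake in the cornea only and is an efficacy endpoint.
- *MGD score.* It runs from 0 to 15 but covers five central lower-lid glands and is exploratory.
- *Description.* It is required at the slit lamp only for clinically significant findings, so a milder baseline abnormality may leave no text to compare with. The funduscopy procedure asks for abnormal findings to be described without that limit.

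The conjunctiva, and the lid beyond five glands, have no other graded measure.

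**The case against.** The strongest reply is that harm is meant to be found through the primary endpoint. A new clinically significant corneal or lid finding fits the adverse event definition and would be tabulated by severity and by eye whatever its slit-lamp grade. Staining and the MGD score grade part of the same tissues at every clinic visit. Clinical significance is already recorded in the description, so the three categories could be partly recovered. The shift table is itself an inference: both analysis sections say only where appropriate, and no table layout or eCRF is in the documents. All of this stands, and it confines the point to the slit-lamp summary.

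A reader might go further and infer that worsening of lids or cornea cannot appear as a shift at all, or that the summary is bound to look reassuring. The documents do not support that. A structure graded Normal at baseline can still shift, and nothing says how many were Abnormal. Nor do the percentages show that the trial would miss harm. The statement in section 10.3 is about adverse events, which do not depend on this grade, and with 200 subjects and half of eyes Abnormal the chance is still about 95%.

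The reply does not make the two-level summary able to separate a new clinically significant finding from an old mild one.

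**Conclusion.** The point holds as a limit of one secondary safety summary. For any structure Abnormal at the NVU-003 baseline, a new clinically significant finding is not visible in the slit-lamp grades. This follows from the scale and the baseline definition alone and needs no assumption.

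The size is not known. For a 3% rate of worsening, the illustrative chance of at least one visible shift runs from 95.2% down to 0% in 100 completers, and from 99.8% down to 0% in 200 subjects. It depends on the assumed baseline share, on the denominator, and on worsening being independent of baseline grade. The sample size and the overall detection of adverse events are not in question. This is a cheap improvement, not a flaw that undermines the trial.

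**What to change.** In Appendix 3 and the eCRF, code each structure in each eye as Normal, Abnormal not clinically significant, or Abnormal clinically significant. Investigators already make this judgement for exclusion 2 and when deciding what to describe.

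In section 10.4.6, add a table per structure, for study and fellow eye separately, of subjects with a first clinically significant finding after NVU-004 Day 1. State there how shifts from the NVU-003 baseline will be shown. The table can be read as new findings because exclusion 2 bars clinically significant findings at Visit 1, whatever scale NVU-003 used. The synopsis wording of exclusion 2 is limited to the ocular surface, so for anterior chamber, iris and lens this reading rests on section 5.4. The two wordings should be reconciled.

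The cost is one extra field, or coding of descriptions already recorded, and one table. Two limits remain. Shifts against the NVU-003 baseline stay two-level if NVU-003 used that grade, and worsening within the not clinically significant category stays unseen.
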